#### Population

• *Inclusion criteria*: Diagnosis of ET, as decided by the movement disorder specialist; Substantial incapacity; Duration of symptoms > 5 years; Age 18 – 75; unsatisfying effect from  $\beta$ -blockers, or be unable to tolerate the medical therapy.

• *Exclusion criteria*: Cognitive impairment; Co-morbidity or non-compliance likely to jeopardize the result or to confuse the evaluation; Normal surgical exclusion criteria.

## Endpoints

Primary outcome measure

[figure not shown]
• ETRS

Secondary outcome measures

- Quality of life in ET (QUEST)
- Neuropsychological tests
- Electric energy consumption

#### Chronology of assessments/investigations

ETRS, QoL, electric energy consumption: baseline, 6, 12, 24, 36, 48, 60, 120 months. Neuropsychological tests: baseline, 12 months

[figure not shown]

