## **PROJECT DESCRIPTION**

#### Overview - What are we going to study?

The effect of DBS for ET will be evaluated in a multicentre study recruiting 100 patients randomized to immediate surgery (group A) or best medical treatment only (as decided by the movement disorder neurologist, with few exceptions likely to be identical to their current medication) with delayed surgery at 6 months if still needed /indicated (group B). Primary outcome is tremor reduction as measured with Essential tremor rating scale (ETRS), with focus on items 5/6 (hand tremor) & 11-14 (hand function), at baseline before surgery and at 6 months. Secondary outcome includes quality of life measured with QUEST and electrical energy consumption. After 6 months group B is operated –as indicated-, and group A and B are thereafter evaluated as one single group for long-term effects and analyses of electrode location. The electrodes will in all patients be inserted with a trajectory developed for this study allowing stimulation both in the established and traditionally used target Vim as well as in the new target cZi. Each contact will be evaluated individually concerning location, effects and side effects, in relation to stimulation parameters. This is done in order to, a) compare the two targets, but more importantly, b) to create a map of the whole area with identification/delineation of the optimal target point/volume. The time necessary to gather

100 patients is estimated to 2.5 - 3 years.

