#### Study design:

- Step 1 is designed as a randomized controlled trial in order to compare the effect of DBS (Group A) and medical treatment (Group B) on ET (Aim 1).
- In step 2 4 the patients in group A are operated and group A and B joined into one single group.
  - Step 2 all electrode contacts are individually analysed regarding chronic and acute stimulation effects in relation to their location in either the Vim or the cZi in order to decide which target is more effective (Aim 2).
  - Step 3 Effects and side effects, with consideration to field of stimulation, are analyzed in relation to neighboring structures in order to map the whole area and delineate the optimal target points (Aim 3).
  - Step 4 The long-term effect is evaluated in a non-randomized longitudinal study at 1, 3, 5, 10 years (Aim 4).

#### 0

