## PRELIMINARY RESULTS

We have in a number of previous studies evaluated DBS for ET in both the Vim and cZi. These studies have analysed effects, complications, long-term outcome, quality of life and effects and side effects in relation to electrode location. Unfortunately, these are non-randomized and/or small studies. However, it seems quite clear that the effect of cZi DBS is promising: in a recently submitted manuscript about 50 patients we could demonstrate an improvement of contralateral tremor and hand function by 86% after 12 months. The contact evaluation demonstrated that the best effect was achieved within the target area itself, and that this target area is clearly distinct from the Vim. We have previously demonstrated in non-randomized longitudinal studies that the effect of cZi is superior to Vim DBS, where the tremor reduction in the latter target was only 60%, and that the electrode contacts with the best effect in what was called Vim were actually placed below the Vim, in the cZi area.

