## ETHICAL CONSIDERATIONS

Patients will be offered participation in this study only after the patient has been accepted for surgery with DBS. Thus, patients not included in this study will anyhow undergo the same

procedure. The surgery with combination of the two targets is an improvement of the procedure, which has been done since 2004 in Umeå. The evaluations performed before and after surgery are normal clinical practice and will not differ between patients participating in the study and patients not participating in the study. Minor differences in the evaluations exist today between the participating clinics, why minor changes of the standard clinical protocol will be necessary at some clinics.

The difference between normal clinical practice and this study is the randomisation into two groups, with immediate/delayed surgery. However, considering that the average waiting time for DBS is longer than 6 months, this does in reality mean that one of the groups will have a normal waiting time, while the other will have a shorter waiting time than normal. The patients who are randomized to delayed surgery will further have one additional evaluation (6 months after randomization) compared to a patient not participating in this study.

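### Should the neuropsychological tests also be given at 6 months, the only time at which DBS and no DBS can be compared as randomised?

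*Protocol*

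**What the plan says.** The Protocol's Overview describes "100 patients randomized to immediate surgery (group A) or best medical treatment only", with the primary tremor outcome at baseline and 6 months and delayed surgery for group B from 6 months where still indicated. From then on, "group A and B are thereafter evaluated as one single group for long-term effects and analyses of electrode location".

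The Endpoints section lists "Neuropsychological tests" among the secondary outcomes. The Chronology section gives two lines:

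- "ETRS, QoL, electric energy consumption: baseline, 6, 12, 24, 36, 48, 60, 120 months"
- "Neuropsychological tests: baseline, 12 months"

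Under Ethical considerations, the evaluations before and after surgery are described as normal clinical practice, the same for participants and non-participants apart from minor harmonisation at some clinics. The exception is that patients in the delayed arm "have one additional evaluation (6 months after randomization) compared to a patient not participating in this study".

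**The concern.** Tremor and quality of life are measured at 6 months, when one arm has been operated and the other has not. Cognition is not. The only post-baseline battery comes at 12 months, when group B may have been operated and the arms are analysed together. A 12-month change from baseline mixes any effect of surgery and stimulation with practice and the passage of time. Practice gain could hide a decline, or a gain could be credited to DBS. A larger sample does not remove that bias, and no later analysis can restore a control arm that has been operated. Since both arms already have a 6-month assessment, the protocol seems to give up a controlled comparison that was within easy reach.

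**Working it through.** **1. Does any cognitive test fall in the randomised window?**

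| Item | Protocol section | Time |
|---|---|---|
| Randomised DBS v no-DBS comparison | Overview; Study design, step 1 | 6 months |
| Group B eligible for surgery, arms pooled | Overview | after 6 months |
| ETRS, quality of life | Chronology | baseline, 6, 12 months and later |
| Neuropsychological tests | Chronology | baseline, 12 months |

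None does: 0 of 1 post-baseline test points. The figure missing from the Chronology section does not affect this, because the text gives the times. Counted from surgery, 12 months yields a before-after change. Counted from randomisation, it compares about 12 months of DBS with about 6. Patients in group B still unoperated by then would be selected by the indication rule and would not be a valid control.

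**2. What does the protocol claim?** Its only power figure for the randomised step is 100%, for the tremor items. Read as proportions, 85% v 25% with 50 per arm and two-sided 5%, this reproduces: power 0.9999998. It says nothing about cognition, and no figure is given for the neuropsychological tests.

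**3. What would a 6-month battery yield?** From the Protocol: 100 patients, less than 5% loss, two-tailed t-test, 95% confidence. Assumed: 1:1 allocation, retest correlation r = 0.7 (range 0.5 to 0.8), one score standing for the battery.

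T-test on change, in SD units: SE = √(2(1 − r) × 2/50)

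| r | SE | 95% CI half-width (1.96 × SE) | Difference with 80% power (2.80 × SE) | Power for 0.3 SD |
|---|---|---|---|---|
| 0.5 | 0.200 | 0.39 | 0.56 | 32% |
| 0.7 | 0.155 | 0.30 | 0.43 | 49% |
| 0.8 | 0.126 | 0.25 | 0.35 | 66% |

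Adjusting for baseline, with 47.5 per arm after 5% loss, SE = √((1 − r²) × 2/47.5). The difference with 80% power becomes 0.50, 0.41 or 0.345 SD for r = 0.5, 0.7 or 0.8. Power for a 0.2 SD difference is only 20% to 37%.

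**4. What does the planned before-after analysis yield?** With n = 100 and r = 0.7, SE = √(2 × 0.3/100) = 0.0775 SD. For a true 0.3 SD decline and a practice gain g, the probability of a significant decline is Φ((0.3 − g)/0.0775 − 1.96):

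| g (SD) | 0 | 0.1 | 0.2 | 0.3 |
|---|---|---|---|---|
| Probability | 97% | 73% | 25% | 2.5% |

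This equals the arm contrast's 49% at g = 0.15 SD. Below that the before-after test has more power, though a change still could not be attributed to DBS. The calculation takes all 100 as operated and followed, which is an upper bound given the indication rule and the allowed loss.

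**5. What would it cost?** Two batteries in 100 patients make about 200 planned sessions. A third adds up to 100, half as many again, across six departments. The length of the battery is not given, and the 6-month assessment already includes ETRS on and off medication and stimulation.

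**The case for a change.** The best argument for change is that assessment times are fixed in the protocol and data not collected cannot be recovered by any analysis plan. Neuropsychological tests are a listed secondary outcome of a brain implant trial; a 6-month date already exists in both arms; and practice would largely cancel between the arms if the test intervals match. The protocol itself treats 6 months as long enough to judge the main effect of DBS. All of this stands, and so does the bias shown for the before-after change.

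It falls short of a defect for these reasons:

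- None of the four aims mentions cognition. The Overview of the randomised trial names quality of life and energy consumption as secondary outcomes. A baseline and 12-month schedule fits the pooled follow-up.
- Preliminary results says of the group's earlier work, "Unfortunately, these are non-randomized and/or small studies". Cognition is not among the topics listed there, so this regret does not show that the trial set out to provide controlled cognitive data.
- An existing assessment date does not mean that no visit is added. The Protocol does not say who gives the battery, where, or for how long.
- A research-only battery in both arms would go beyond the one exception that the ethical section makes to routine evaluation.
- The contrast would need a stated stimulation and medication state in group A and the same clock in both arms. Blinded video rating is described for tremor only. A third session would also add practice to the planned 12-month result; parallel test forms would reduce this but might not remove it.

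**Conclusion.** The observation is correct, but no change follows. The schedule provides no randomised DBS v no-DBS comparison of cognition, and the Protocol promises none. The primary outcome and Aims 1 to 4 are unaffected.

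Adding the battery is an option for a sponsor with the resources, not the repair of an error. It would exchange up to 100 extra sessions, a revised ethical premise and more practice in the 12-month result for an estimate with a 95% CI half-width of about 0.30 SD (0.25 to 0.39) and 49% power (32% to 66%) for a 0.3 SD difference. That could inform but would not establish cognitive safety. These figures rest on an assumed 1:1 split, retest correlation, effect size and presence of the effect by 6 months. The count of 0 test points in the randomised window rests on no assumption.

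What remains is a matter of reporting: the 12-month cognitive results should be described as a before-after change or, if 12 months runs from randomisation, as immediate versus delayed surgery. They should not be read as a randomised effect of DBS against medical treatment.

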#### Surgery

[figure not shown]
The patients are implanted using a trajectory targeting both the traditional target in the Vim and the new target in the cZi, with electrode contacts in both structures. Variations in the anatomy of the individual patient in combination with random deviations from the intended target point, will guarantee a spread of electrode contacts through the area of interest (Figure 3).

## **Evaluation of stimulation**

Tremor is measured with  $ETRS^{11}$  (with focus on items 5/6 (hand tremor) & 11-14 (hand function). ETRS is performed before surgery at baseline and at 6 months on/off med/stim. The evaluation is done blinded to the patients in the surgical group. The evaluation is documented on video (with the patient wearing a head cap) and

segmented for blinded evaluation of two expert evaluators. In the second step all individual electrode contacts are evaluated in the same manner regarding tremor, but also regarding side effects, with standardized stimulation parameters and a gradual increase of voltage (Figure 4).

#### **Target analysis**

All individual electrode contacts are evaluated as described above (Figure 4). In all patients a preoperative MRI (with tractography) and a postop MRI/CT are performed under stereotactic conditions, allowing fusion of the images. The exact location of each contact is determined in relation to multiple neighbouring structures, among other structures, the anterior and posterior commissures, the center of the red nucleus, the posterior tip of the STN and the cerebellothalamic fiber bundle as identified on tractography. The analysis is performed using the Framelink navigation tool by two experts. The contacts are plotted on stereotactic atlases and 3D models created. The contacts are further classified according to their location and effects/side-effects. The electrical properties of the area surrounding each contact are analysed, and the stimulation parameters are documented in order to map the actual field of stimulation. Based on these data the different targets can be outlined with respect to optimal effects/lack of side effects and maps of the area created.

This is done to outline the optimal target, to provide a map for preoperative planning of the electrode location; to provide a map for interpretation of peroperative findings of macrostimulation and further to develop optimal stimulation strategies.

Further, we have within the EU FP-7 IMPACT project developed a computorized model with automatic segmentation of the target area based on the MRI of the individual patient for targeting and a stimulation model based on the location of the electrode. This model will in the current project be adapted to the VL-thalamus/PSA and tested against best clinical practice. Hopefully, this will be of help for the non-expert regarding targeting, and reduce the necessary time for optimization of stimulation parameters.

#### **Statistics:**

Two-tailed T-test will be used for continuous variables, Wilcoxon signed rank test for paired non-parametric data and Mann-Whitney U test for un-paired non-parametric data. The model of stimulation fields, Volumes of Neural Activation (VNAs), will be generated using simulations of homogeneous tissue with density compensated probabilistic stimulation

maps. Registercentrum Norr will be responsible for the statistical analyses and stimulation field analysis will be done by Medtronic Eindhoven Design Center for Neuromodulation.

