## Sample size and power:

In step 1, with a confidence interval of 95%, and an expected improvement of 85 % in the surgical group and none (or at least < 25%) in the medical group, regarding contralateral items 5/6 & 11-14, a power of 100 % is achieved. In step 2, with an expected improvement of 85% in one target and 60% in the other, a power of 98% is achieved. The high number of patients is, however, necessary for step 3, mapping of the area, in order to give a good cover of the periphery (Length of contact carrying electrode surface 7.5 mm, expected mean non-random intended deviation from target point (as defined in the study) 1 mm, expected mean random deviation from intended target point 1.5 mm). Based on the previous experience, less than 5% of patients is expected to be lost during the follow up, which will have an insignificant effect on the power.

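### Baseline adjustment of 6-month QUEST would sharpen the randomised comparison at no data cost, but the protocol lists only unadjusted between-group tests; for ETRS the gain is conditional and changes no conclusion

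*Protocol*

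**What the plan says.** The protocol's Statistics section assigns tests by type of data: "Two-tailed T-test will be used for continuous variables", the Wilcoxon signed rank test for paired data, and "Mann-Whitney U test for un-paired non-parametric data". The comparison of immediate with delayed surgery is unpaired, so it falls to the t-test or Mann-Whitney. No covariate, ANCOVA or regression model appears anywhere in the protocol.

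The section on chronology of assessments schedules "ETRS, QoL, electric energy consumption: baseline, 6, 12, 24, 36, 48, 60, 120 months". The section on evaluation of stimulation adds "ETRS is performed before surgery at baseline and at 6 months on/off med/stim". Ethical considerations states that the delayed-surgery group has an extra evaluation 6 months after randomisation, without listing its instruments.

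The Overview says "Secondary outcome includes quality of life measured with QUEST"; no effect size or power is given for it. For ETRS, Sample size and power assumes "an expected improvement of 85 % in the surgical group and none (or at least < 25%) in the medical group", "regarding contralateral items 5/6 & 11-14", and concludes "a power of 100 % is achieved". The protocol does not say whether the tested quantity is the 6-month score, the absolute change or the percentage improvement.

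**The concern.** When an outcome is measured before randomisation and again at the endpoint, part of the endpoint's variation is predictable from the first measurement. An unadjusted test of the 6-month score leaves that variation in the error term. A test of the change score removes it with a fixed slope of one, which over-corrects unless the correlation is very high. ANCOVA estimates the slope.

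The stake is the width of the interval around the treatment effect. For QUEST, which has no stated power, it may also decide whether a moderate difference is detected.

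**Working it through.** **The plan's own figure.** Taking the ETRS percentages as proportions (85% versus 25%, 50 per arm, two-sided 5%) gives power 0.9999998, in line with the stated 100%. Taking them as means 60 points apart, power is still 99.9% at an SD of 60 points. ETRS significance is therefore not in question.

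**Inputs.**
- From the protocol: 100 patients, two arms, two-sided test, 95% confidence, loss below 5%.
- Assumed: 1:1 allocation (50 per arm), r from 0.3 to 0.8, equal SDs unless stated, and a QUEST difference of 0.5 SD.

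**CI width.** In units of the squared SD, the variance of the between-group difference is (2/n) times:
- 1 for the 6-month score;
- 2(1 - r) for the change score;
- 1 - r² for ANCOVA.

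The CI ratio for ANCOVA is therefore √(1 - r²) against the 6-month score and √((1 + r)/2) against the change score.

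| r | narrower than 6-month score | narrower than change score |
|---|---|---|
| 0.3 | 1 - √0.91 = 5% | 1 - √0.65 = 19% |
| 0.5 | 1 - √0.75 = 13% | 1 - √0.75 = 13% |
| 0.7 | 1 - √0.51 = 29% | 1 - √0.85 = 8% |
| 0.8 | 1 - √0.36 = 40% | 1 - √0.90 = 5% |

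With t quantiles and the small-sample ANCOVA factor, the half-widths at r = 0.5 are 0.397 SD for either unadjusted score and 0.346 SD for ANCOVA, which is 12.9% narrower. At r = 0, ANCOVA is about 0.5% wider than the 6-month analysis; that is the price if baseline predicts nothing.

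**QUEST power for a 0.5 SD difference.** This uses the noncentral t with 98 df unadjusted and 97 df for ANCOVA. The noncentrality is 0.5/√(factor × 2/50). At r = 0.5 that is 0.5/0.2 = 2.50 for either unadjusted score and 0.5/(0.2 × √0.75) = 2.89 for ANCOVA.

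| r | 6-month score | change score | ANCOVA |
|---|---|---|---|
| 0.3 | 69.7% | 55.3% | 73.7% |
| 0.5 | 69.7% | 69.7% | 81.5% |
| 0.7 | 69.7% | 89.2% | 93.4% |
| 0.8 | 69.7% | 97.5% | 98.5% |

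Simulating Mann-Whitney on normally distributed 6-month scores gives about 67%. With 5% loss (47.5 per arm) at r = 0.5, the figures are 67.4% unadjusted and 79.5% with ANCOVA.

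The gain shrinks with a larger effect. At r = 0.5 and 50 per arm it is 93% versus 98% for 0.7 SD, and 98% versus 99.6% for 0.8 SD.

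**Unequal SDs.** The setting was a surgical-arm SD of 0.6 to 1.2 times control, r from 0.3 to 0.8, and 20,000 runs per setting, comparing Welch t-tests with ANCOVA using HC3 standard errors. ANCOVA was 4-40% narrower than the 6-month score and 1-28% narrower than the change score.

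**ETRS.** Sixteen simulated scenarios used the protocol's mean improvements (85% versus 0% or 25%) with assumed spreads and scores floored at zero. ANCOVA was 4-24% narrower than the 6-month score and 8-28% narrower than the change score. Against a t-test of percentage improvement, a rerun put its effect divided by standard error at 0.77 to 1.11 times that of the percentage test, lower in 8 of 16 scenarios. The effect was at least 8.5 standard errors under every analysis.

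**The case against.** The strongest objection is one of scope. Covariates are often left to a statistical analysis plan, none is shown here, and a one-line list of tests does not exclude adjustment. That limits the point to an optional improvement. It does not remove it, because the protocol itself chooses the between-group tests and each one it lists is unadjusted. If an analysis plan already specifies ANCOVA, the protocol sentence should be aligned with it.

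The second objection concerns ETRS, and it largely stands. The Overview speaks of tremor reduction, and the sample-size section plans in percentages, so percentage improvement is the likelier tested quantity. There the simulations show no consistent gain and sometimes a loss. The word contralateral also has no reference side in an arm that is unoperated at 6 months. A reader might infer that baseline adjustment is a free gain for the primary outcome; the protocol does not support that.

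Third, the 0.5 SD difference and r come from outside the protocol. This is true, so the results are given as ranges. Against change scores at r = 0.8 the power gain is only 1 percentage point. It is also fair that the extra evaluation in the delayed arm is not said to include QUEST. That rests on the assessment schedule, which makes no distinction by arm.

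**Conclusion.** The point holds as a low-priority improvement centred on QUEST. Under the assumed r of 0.3 to 0.8, ANCOVA gives a 95% CI 5-40% narrower than the 6-month score and 5-19% narrower than the change score. For a 0.5 SD difference at r = 0.5, it raises power by about 12 percentage points over the t-test, and by slightly more over Mann-Whitney.

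Two stronger readings are tempting. One is that unadjusted tests bias the comparison; under randomisation they do not. The other is that the primary conclusion is at risk; with stated power of 100% and an effect of many standard errors under every analysis, it is not.

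**What to change.** Add to Statistics that 6-month QUEST is compared between the randomised groups by ANCOVA with baseline QUEST as covariate and robust (HC3) standard errors, reporting the adjusted mean difference with its 95% CI. Keep the Mann-Whitney test as a sensitivity analysis.

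For ETRS, first state which quantity is tested. If it is the 6-month score or the absolute change, use the same baseline adjustment, name which of the on/off assessments supplies the score, and score the items on a side fixed in advance by the same rule in both arms. If it is percentage improvement, no change is asked for on this ground.

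The QUEST change costs one or two sentences. The ETRS part needs a little more, because the side and the assessment state have to be defined. Neither requires new data, visits or patients.

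### For Aim 4 the only listed tests that fit are paired tests, which leave out patients lost before each late visit, and the expected loss below 5% has no time horizon

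*Protocol*

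**What the plan says.** Under Study design, step 4 reads: "The long-term effect is evaluated in a non-randomized longitudinal study at 1, 3, 5, 10 years". The Overview explains who is in it. Once group B has been operated on, "group A and B are thereafter evaluated as one single group for long-term effects and analyses of electrode location", so there is no control arm after 6 months. The Chronology section schedules "ETRS, QoL, electric energy consumption: baseline, 6, 12, 24, 36, 48, 60, 120 months", which is more visits than the four time points named for step 4.

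The Statistics section lists tests by type of data. It gives a two-tailed t-test for continuous variables, the "Wilcoxon signed rank test for paired non-parametric data", and the Mann-Whitney U test for unpaired data. It names no other method for clinical outcomes and does not tie any test to a particular aim.

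The only statement about loss is under Sample size and power: "less than 5% of patients is expected to be lost during the follow up, which will have an insignificant effect on the power". It closes a paragraph on power for steps 1 and 2 and on the number of patients needed for the mapping in step 3.

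**The concern.** Aim 4 asks whether the effect lasts. A paired test at 10 years needs both the baseline and the 10-year value. A patient seen at 12, 24, 36, 48 and 60 months but not at 120 contributes nothing to it. The comparisons at 1, 3, 5 and 10 years can therefore describe four different and progressively smaller groups.

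If patients whose benefit is fading are more likely to miss late visits, those who remain look better than the whole group, and the effect appears more durable than it is. With no control arm, nothing in the design offsets this. The protocol treats loss only as a matter of power, whereas for a long uncontrolled follow-up the larger risk is bias. The loss figure also gives no help in judging that risk, because it does not say what period it covers.

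**Working it through.** **Inputs from the protocol.** 100 patients (Overview); expected improvement of 85% against 60% with 98% power in step 2, and loss below 5% (Sample size and power); last visit at 120 months (Chronology); entry at age 18 to 75 (Population), so up to 85 at the last visit.

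**1. The plan's own figures.** No standard deviation is given, so the percentages are treated as proportions at two-sided alpha 0.05.
- Step 1, 85% against 25%, 50 per group assumed: power 0.9999998, matching the stated 100%.
- Step 2, 100 per target: power = Φ[(0.25 − 1.96 × √(2 × 0.725 × 0.275/100)) / √((0.85 × 0.15 + 0.60 × 0.40)/100)] = Φ[(0.25 − 0.1238)/0.0606] = Φ(2.08) = 0.981, matching 98%.
- Step 2, 95 per target: 0.976.

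The statement that 5% loss hardly affects power is therefore right for step 2. No power is claimed for step 4.

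**2. What 5% means over different periods.** At a constant rate, annual loss = 1 − 0.95^(1/T).

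| Period T | Annual loss |
|---|---|
| 1 year | 5.0% |
| 3 years | 1.70% |
| 5 years | 1.02% |
| 10 years | 0.51% |

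In the other direction, assumed annual loss of 1%, 2% or 3% gives 10-year loss of 1 − 0.99^10 = 9.6%, 1 − 0.98^10 = 18.3% or 1 − 0.97^10 = 26.3%. The protocol gives no rate of death, explantation or dropout from which to choose among these.

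**3. Size of the bias.** The mean among those still observed exceeds the mean of all patients by

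(fraction lost) × (mean improvement of observed − mean improvement of lost).

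The gap between observed and lost is an assumption; 10 to 30 percentage points is shown.

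| Lost at 10 years | Gap 10 | Gap 30 |
|---|---|---|
| 5% | 0.5 | 1.5 |
| 18% | 1.8 | 5.4 |
| 40% | 4.0 | 12.0 |

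**4. Simulation, all values assumed.** 100 patients per trial, 200 trials per scenario; mean improvement falling 2 points per year from 80% at year 1, so 80 − 2 × 9 = 62 at year 10; intercept SD 12, slope SD 1.5, residual SD 8; loss depending on the last observed improvement (at least 70%, or below).

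| Annual loss (≥70% / <70%) | Lost | Completer mean | True mean | Excess |
|---|---|---|---|---|
| 2% / 6% | 27% | 63.8 | 62.1 | 1.7 |
| 3% / 10% | 40% | 65.2 | 62.0 | 3.2 |

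A likelihood model on all visits gave 62.0 in both scenarios. With loss unrelated to effect, both methods were unbiased. By the formula in step 3, the simulated gaps are 1.7/0.27 = 6.3 and 3.2/0.40 = 8.0 points. The simulation is thus a milder case than the 10 to 30 points tabulated.

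**The case against.** The strongest objection is that the Statistics section is one generic sentence. It does not assign a test to Aim 4, does not prescribe visit-by-visit testing and sets no completer rule. Missing-data handling and longitudinal models usually belong in a statistical analysis plan, which is not shown. This stands in part: it would be wrong to say that the protocol prescribes completer tests for Aim 4, and the absence of a missing-data method is no finding. But the section does commit to named tests, and only the paired ones fit a before-after comparison in one group. An analysis plan that kept to the list would produce completer comparisons.

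Three stronger readings are tempting, and the document does not support them.
- A reader might infer that the 24- and 48-month data go unused. The Chronology section collects them and step 4 does not name them, but nothing says they are left out.
- A reader might infer that the protocol promises loss below 0.51% per year. That holds only if the undated 5% covers all 120 months, and its place after the power for steps 1 and 2 suggests a shorter period.
- A reader might infer that the 5% is wrong. Entry up to age 75 makes it doubtful over 10 years, but it is said to rest on previous experience and no figure in the protocol contradicts it.

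It is also fair that the simulation favours the mixed model, because loss depended on observed values, the condition under which a likelihood model is unbiased. Frailty, death or explantation need not meet that condition. With no visit between 60 and 120 months, decline in that interval may never be recorded before a patient is lost.

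**Conclusion.** The point holds as a weakness in the stated method. The tests listed for clinical outcomes suit Aim 4 poorly, because those that fit discard earlier data from patients since lost. That late benefit would be overstated is conditional: it needs loss related to fading effect, which the protocol does not address.

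Under that assumption the overstatement is modest: about 2 to 3 points in the simulation at 27% to 40% loss, and about 0.5 to 1.5 points at 5% loss with a gap of 10 to 30 points. It would be larger only if substantial loss came with a wide gap. In the simulation most of the decline would still be seen; with 27% lost, completers show 80 − 63.8 = 16.2 of the 18 points.

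Separately, the loss figure lacks a period and is discussed only for power. Whatever period was meant, the protocol should say so: if it is short, step 4 has no expected loss at all; if it is 120 months, the implied 0.51% per year needs a basis. Neither matter affects the randomised 6-month comparison.

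**What to change.** **Statistics.** Name for Aim 4 a linear mixed model for repeated measures. The outcome is change in ETRS from baseline at every scheduled postoperative visit, with time since surgery, baseline ETRS as covariate, and within-patient correlation (patient as random effect or unstructured covariance). Time since surgery matters because group B is operated on about 6 months later than group A. Report the contrasts at 1, 3, 5 and 10 years, and keep the paired completer tests as a sensitivity analysis. State that the model assumes loss is explained by observed values, and report the numbers observed, deaths and explantations beside each time point. The model reduces bias from outcome-related loss but does not guarantee its removal.

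**Sample size and power.** State the period that the 5% covers and give step 4 its own expected loss, with its basis, discussed as a possible source of bias as well as of lost power.

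**Cost.** Two short wording changes and slightly more analysis work. No new visits or data are needed. The price is reliance on the missing-at-random assumption, and the stated loss for step 4 may look less favourable.
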